3.10 Sample size

WHO advises that sentinel surveillance should cover at least 1-2% of a population [1]. Current active sites as described in section 3.2 cover between 6.8% (Germany) to 16.2% (Belgium) of their countries' population. The primary objective of this surveillance study is to determine the proportion of relevant pathogens among the admitted SARI patients. Through a feasibility assessment, we anticipate recruiting 300 patients per hospital, totalling 6,600 SARI patients (300 patients per hospital across 22 hospitals) for the upcoming season. Further assuming a 10% drop-off rate, the final patient size is estimated to be around 5,940. Table 4 below demonstrates the anticipated precision (by Binomial Exact method at 95% confidence interval) regarding the prevalence corresponding to the expected proportion of each primary pathogen of interest.

Confidential Version 1.0

Dathagan of	Minimum expectation		Maximum expectation	
interest	Prevalence case among admitted SARI patients	Precision	Prevalence case among admitted SARI patients	Precision
COVID	20%	1.025%	25%	1.109%
RSV	2%	0.365%	7%	0.657%
Influenza	7%	0.657%	12%	0.835%

Table 4. Anticipated precision regarding the prevalence corresponding to the expected proportionof the pathogens of interest

The precision provided by this patient size is within an acceptable range. The precision will increase if the actual enrolled patient size is smaller than expected. Further sample size justifications for the other objectives will be provided in the SAP.

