3.13.2 Total SARI and pathogen-specific SARI numbers

The total number and proportion of positive laboratory samples for each respiratory pathogen of interest (see section 3.8.1) and co-infections (see section 3.6.4) will be provided. Counts and proportions (%, along with 95% exact binomial confidence intervals) will be provided by calendar time, by Study Contributor, by country and by age- and risk groups of interest. Co-infections (%) will be described, by number of pathogens, by pathogen type and by healthcare utilisation outcomes. Visualisations of these counts and percentages over time will be provided.

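### Table 4 and the pooled exact binomial intervals allow nothing for clustering by hospital, so they are too narrow if the results are meant to apply beyond the 22 participating hospitals

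*Protocol*

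**What the plan says.** Section 3.10 plans "300 patients per hospital across 22 hospitals", which is 6,600. It then continues: "Further assuming a 10% drop-off rate", "the final patient size is estimated to be around 5,940". For this total, "Table 4 below demonstrates the anticipated precision (by Binomial Exact method at 95% confidence interval"), and the section judges the resulting half-widths acceptable. It leaves to the SAP only the sample size justification for the other objectives.

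Section 3.13.2 sets the analysis: "Counts and proportions (%, along with 95% exact binomial confidence intervals) will be provided by calendar time, by Study Contributor, by country", and also by age and risk group. Apart from single-hospital contributors, these strata pool hospitals.

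The protocol mentions no design effect, ICC, site effect or cluster-robust variance. It does describe differences between sites:
- Table 1: recruitment through the emergency department, infectious disease wards or hospital records.
- Table 2 and section 5: different assays, with a warning about comparability across sites.
- Section 5: a share of SARI captured that varies by contributor.
- Footnote to Table 3: one five-hospital contributor excludes long-term care residents.

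Section 3.10 closes its precision statement with "The precision will increase if the actual enrolled patient size is smaller than expected".

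**The concern.** An exact binomial interval is valid for independent patients who share one probability of testing positive. Here patients come in groups of about 270 per hospital, and the protocol's own account of the sites makes a common probability hard to defend. If positivity differs between hospitals and the hospitals stand for a wider population, the pooled proportion varies more than the binomial formula allows.

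At stake are the error bars of the first primary objective. The comparison most exposed is between countries. Belgium has 2 hospitals and Germany 3, so a difference between a few hospitals can be read as a difference between countries.

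**Working it through.** **Inputs.** From section 3.10: 300 patients per hospital, 22 hospitals, 10% drop-off, and the Table 4 prevalences. From Table 1: hospitals per country are Spain 10, Italy 7, Belgium 2 and Germany 3, total 22. Assumed, because the documents give none: ICC of 0.001, 0.005, 0.01 and 0.02, and equal hospital sizes.

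**Step 1: reproduce Table 4.** N = 300 × 22 × 0.9 = 5,940. The half-width is (upper − lower)/2 of the Clopper-Pearson 95% interval.

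| Prevalence | Table 4 | Recomputed, N = 5,940 | Recomputed, N = 6,600 |
|---|---|---|---|
| 2% | 0.365 | 0.3651 | 0.3457 |
| 7% | 0.657 | 0.6575 | 0.6232 |
| 12% | 0.835 | 0.8349 | 0.7915 |
| 20% | 1.025 | 1.0255 | 0.9725 |
| 25% | 1.109 | 1.1094 | 1.0521 |

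All five agree with Table 4 at 5,940 to within 0.001 points. The arithmetic is right, and it uses a design effect of exactly 1.

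**Step 2: add clustering.** Patients per hospital m = 300 × 0.9 = 270. Design effect = 1 + (m − 1) × ICC = 1 + 269 × ICC. Effective N = 5,940 / design effect. The Clopper-Pearson half-width is then recomputed at the effective N. Coverage is that of the unadjusted exact interval in a beta-binomial simulation (22 hospitals of 270, 20,000 runs, prevalence 2%, 7% and 20%).

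| ICC (assumed) | Design effect | Effective N | Half-width at 20% | Half-width at 7% | Coverage of nominal 95% |
|---|---|---|---|---|---|
| 0 (Table 4) | 1 | 5,940 | 1.025 | 0.657 | about 95% |
| 0.001 | 1.27 | 4,681 | 1.16 | 0.74 | about 92% |
| 0.005 | 2.3 | 2,533 | 1.58 | 1.01 | about 81% |
| 0.01 | 3.7 | 1,610 | 1.98 | 1.28 | about 70% |
| 0.02 | 6.4 | 931 | 2.62 | 1.69 | about 57% |

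For scale, the between-hospital SD is √(ICC × p × (1 − p)). At p = 0.20 and ICC 0.01 this is √(0.01 × 0.16) = 0.04, or 4 points.

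**Step 3: country strata.** The design effect depends on patients per hospital, not on the number of hospitals, so a country with 2 or 3 hospitals of 270 has the same design effect. Simulated coverage at ICC 0.01 is again about 70%.

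**Step 4: monthly strata.** 270 / 12 is about 22 patients per hospital per month. Design effect = 1 + 21 × ICC = 1.02, 1.1, 1.2 and 1.4 over the four ICC values. Coverage stays at roughly 90% or above even at ICC 0.02.

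**Step 5: the 22 hospitals as the whole target.** With the hospital probabilities held fixed and the target set to their mean, the pooled exact interval covers about 95.5%. There is no under-coverage on that reading.

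**The case against.** The strongest reply is that the sites are named and selected, not sampled, and that the first objective is descriptive. If the target is SARI patients at these 22 hospitals, the exact interval does its job (step 5). That stands as a condition on the point. It does not remove the point: the title sets the study across Europe, and sections 3.10 and 5 justify the network by its coverage of national populations, which is a claim beyond these hospitals.

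It is also fair that the sample size comes from a feasibility assessment with no precision threshold, that results by contributor and country will make heterogeneity visible, and that the sample proportions are unaffected. All of this limits the consequence. A SAP could add clustering, but the protocol has already named the interval for the primary objective.

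Four stronger readings are tempting and are not supported:
- **Spurious differences between months or pathogens.** The same hospitals contribute to every month and every pathogen. In simulation with a stable hospital effect and 22 patients per hospital per month, a naive test of a month difference rejects about 5% of the time. Variation by hospital within month could change this, but the documents give no figure for it.
- **Full-pool inflation in monthly strata.** Step 4 shows that it is far smaller at the same ICC.
- **An ICC taken from Table 4's RSV range of 2% to 7%.** That range is the minimum and maximum expectation for overall prevalence, not the spread between hospitals.
- **The closing sentence of 3.10 as a calculation error.** Table 4 uses precision to mean half-width, and in that sense the sentence has the right direction. The fault is wording: most readers will take it as saying that fewer patients give better estimates.

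**Conclusion.** The point holds, conditionally. Table 4 and the intervals in 3.13.2 that pool hospitals assume independent patients, which the protocol's own site descriptions make implausible. For inference beyond the participating hospitals, the full-period pooled and country intervals are too narrow: by a factor of about 1.1 at ICC 0.001 (1.16/1.025) and about 2.6 at ICC 0.02 (2.62/1.025), at 20% positivity. The coverage figures of 92% down to 57% rest on assumed ICCs, equal hospital sizes and a beta-binomial model. They show a range and are not a forecast of actual coverage.

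The contrasts at risk are those between countries. Intervals for the two multi-hospital contributors are affected in the same way. Single-hospital results are not. Nothing here shows that the study is too small.

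**What to change.** 1. In 3.10, state whether the proportions are meant to describe patients beyond the participating hospitals, and restate Table 4 with a design effect over an ICC range that includes 0.001.
2. In 3.13.2, keep the pooled sample proportion as the estimate. Where hospitals are pooled, take the interval from a cluster-adjusted method: cluster-robust variance with a t reference on hospitals minus 1, a design-effect-adjusted exact interval, or a random-intercept logistic model. The last must be marginalised to the population proportion, because its intercept alone describes a typical hospital and would change the quantity estimated.
3. For countries with 2 or 3 hospitals, borrow the between-hospital variance from the pooled model.
4. Keep the exact binomial interval for single-hospital results.
5. Reword the closing sentence of 3.10 to say that the intervals will be wider if fewer patients are enrolled.

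The cost is a recomputed table, a paragraph in 3.13.2 and slightly more analysis work. The stated precision becomes less favourable. No extra patients or data are needed.

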3.11 Flow chart of data collection

The figure below indicates the timelines for which data will be collected (Figure 2).

All data are collected from pre-existing medical files (registries and/or patient files), and are therefore considered as a secondary data collection, except for laboratory results that will be collected specifically for the purpose of the study and are considered as a primary data collection (Section 3.5, Section 3.8 and Section 3.9).

Confidential Version 1.0

21 March 2024 Page **33** of **49**

3.12 Data management

Data collection, statistical analysis and preparation of the study report are activities firewalled from Pharmaceutical Company Partners to avoid perception of undue influence on the study report and result interpretation.

3.12.1 Data management at Study Contributor level

Each study site is responsible for the data collection and data management of their participant-level study data. Depending on the study site, the data collection and source documentation will be different. The source for the variables collected in the study is collected during a site initiation visit.

3.12.2 Data flow

- 1. The Study Contributor collects the data and enters/uploads it in the Castor[®] electronic data capture (EDC).
- 2. The Study Sponsor validates the data, raises applicable queries and the Study Contributor responds to data queries by updating or confirming the data.
- 3. The Study Sponsor imports the data from all participating Study Contributors in a secure environment using the EDC system's export functionality.
- 4. The Study Sponsor transforms all data to generate the output as pre-specified in the SAP within the secure environment.

P95 reviews the imported variables on a bi-weekly basis. These data review checks are detailed in the Data Validation Plan.

A data management plan (DMP) is written prior to the start of the data collection to describe data management at the central level. The DMP describes all functions, processes, responsibilities and specifications for data collection, data storage, quality checking, transfer, cleaning, and validation. The DMP is updated regularly. All statistical analyses will be conducted in the id.DRIVE Research Server.

3.13 Data analysis

A SAP will be developed prior to the conduct of the analysis. The SAP specifies all statistical analyses, including sensitivity analyses, to be conducted and will include table shells and mock figures. There will be one common SAP for all Study Requestors.

3.13.1 Attrition diagram

An attrition diagram will be created, describing the number of records excluded from the statistical analyses, by reason of exclusion.

Confidential Version 1.0

21 March 2024 Page **34** of **49**

3.13.2 Total SARI and pathogen-specific SARI numbers

The total number and proportion of positive laboratory samples for each respiratory pathogen of interest (see section 3.8.1) and co-infections (see section 3.6.4) will be provided. Counts and proportions (%, along with 95% exact binomial confidence intervals) will be provided by calendar time, by Study Contributor, by country and by age- and risk groups of interest. Co-infections (%) will be described, by number of pathogens, by pathogen type and by healthcare utilisation outcomes. Visualisations of these counts and percentages over time will be provided.

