Data collected at Study Contributors will be checked for quality and transferred to a dedicated, secured central server hosted by P95. A data management plan (DMP) will be written prior to the start of the data collection. The DMP will describe all functions, processes, responsibilities and specifications for data collection, cleaning, and validation.

Confidential Version 1.0

Ethical considerations

The protocol will be submitted to relevant ethics committee(s) following local regulations. Informed consent will be obtained from participants/guardians as specified by the national/regional ethics committee.

Study limitations

When using sentinel surveillance, generalisability may be limited as social and demographic factors are usually not uniform across a country and thus the catchment population of a sentinel network may not be comparable with the remaining population of a country. Current active sites cover between 6.8% (Germany) to 16.2% (Belgium) of their countries' population, which is above the World Health Organization (WHO) recommended coverage for sentinel surveillance (at least 1-2% of a population) [1].

Under-detection of pathogens of interest may occur. RT-PCR sensitivity is influenced by several factors, including operator sampling technique, type of respiratory specimen, number of specimens collected, and timing of sampling [2, 3]. Assay sensitivity may also vary across pathogens. To limit under-detection, only assays with high sensitivity are used, sampling is performed in the first 72h after hospital admission, and information on the main factors influencing result RT-PCR are collected. Guidance on collecting and handling specimens for the diagnosis of viral respiratory pathogens are given as part of study staff training.

With RT-PCR, a positive result is highly specific for the presence of the viral pathogen nucleic acid of interest. However, RT-PCR does not differentiate between viable and nonviable virus, and a positive result may indicate an older infection, non-causal to the current SARI episode. Notably, as only results of specimens sampled within 72h after admission are included, inclusion of hospital-acquired infections will be avoided.

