2.1 Primary objectives

- 1 To calculate the proportion of laboratory samples positive for each viral respiratory pathogen of interest¹, among adult patients hospitalised with SARI;
- 2 To characterise adult SARI patients (including age, gender, protective- and risk factors, specific treatments, and healthcare utilisation outcomes), overall and by viral respiratory pathogen of interest¹.

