3.6.3 Laboratory-confirmed infection

For each studied pathogen, a laboratory-confirmed infection is a positive reverse transcription polymerase chain reaction (RT-PCR)³ or multiplex RT-PCR on a respiratory specimen(s) collected between 14 days prior to and up to 72 hours after hospital admission. If all samples collected in this time frame are negative, the patient is considered as not having any laboratory-confirmed infection.

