3.13.5 Incidence rates

As part of the exploratory objectives, pathogen-specific SARI incidence rates (per 100,000 personyears) will be calculated and monitored over time to identify trends using the following formula [27]:

 $Incidence \ rate = \frac{\text{Number of events in specified period}}{\text{Average number of persons at risk during the same specified period}}$

The number of events in a specific period will be calculated by multiplying the percentage of SARI patients testing positive for a specific pathogen within the selected time period with the total number of SARI patients (included in the Surveillance Study and missed SARI patients identified by screening logs). Alternatively, the untested SARI events may be accounted for by multiple imputation of expected testing results (e.g., for RSV [2, 3]).

Incidence estimates will not be calculated unless formal denominator mapping can be performed and there is an accurate process for identifying SARI events that were missed by active surveillance. Denominator data will be based on the hospital-reported catchment population of each hospital. The

Confidential Version 1.0 21 March 2024 Page **35** of **49** total number of hospital beds in a region corresponding to the Study Contributor's catchment region will be obtained, and the percentage of hospital beds caught by the specific Study Contributor will be calculated. The percentage of hospital beds caught by the Study Contributor will be used to calculate the hospital's catchment population. The catchment population of each hospital is expected to reflect the average number of persons at risk during that same time period Official regional (or national if not available) population gender- and age-specific distributions will be obtained to model these characteristics for the Study Contributor-specific catchment populations. These modelled data will be used to calculate gender- and age-specific incidence rates of SARI by pathogen. Further, incidence rates will also be adjusted for events missed due to lower diagnostic testing sensitivity of single specimens among older adults as seen in several recent incidence meta-analyses [28, 18]. Details will be provided in the SAP.

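### The unit of the primary proportion is contradictory: objective 1 and section 3.13.2 count laboratory samples, while the outcome definition, sample size and incidence numerator count patients

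*Protocol*

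**What the plan says.** Samples as the unit:

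- Section 2.1, objective 1: "To calculate the proportion of laboratory samples positive for each viral respiratory pathogen of interest". The title page and the abstract carry the same objective.
- Section 3.13.2: "The total number and proportion of positive laboratory samples for each respiratory pathogen of interest", reported "along with 95% exact binomial confidence intervals". The statistical analysis part of the abstract says the same.

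Patients as the unit:

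- Section 3.5 makes laboratory-confirmed infection, in hospitalised SARI patients, the outcome for the primary objectives.
- Section 3.6.3 reduces all specimens in the window to one status per patient: "If all samples collected in this time frame are negative, the patient is considered as not having any laboratory-confirmed infection".
- Section 3.10 restates the primary objective as a proportion among admitted SARI patients and sizes it in patients: "Through a feasibility assessment, we anticipate recruiting 300 patients per hospital, totalling 6,600 SARI patients", reduced to about 5,940 after 10% drop-off.
- Section 3.13.5 builds the incidence numerator from "the percentage of SARI patients testing positive for a specific pathogen".

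More than one specimen per patient is foreseen. Section 3.6.3 accepts "respiratory specimen(s) collected between 14 days prior to and up to 72 hours after hospital admission", section 3.8.2 accepts several specimen types, and the limitations part of the abstract lists "number of specimens collected, and timing of sampling" among the factors affecting sensitivity. Nothing in the protocol limits the primary proportion to one sample or one result per patient.

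**The concern.** Two analysts could follow this protocol faithfully and report different figures for the first primary objective. If the sample wording is taken literally and some patients have repeat swabs, three things follow.

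- **Weighting.** A patient with two samples counts twice.
- **Classification.** A patient confirmed on one swab and negative on another adds a negative to the sample count, although 3.6.3 classes that patient as infected.
- **Interval.** The exact binomial interval assumes independent trials. Swabs from one patient are correlated, so the interval is too narrow.

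Section 3.13.2 also reports the proportion by Study Contributor and country, and under 3.8.2 sampling depends partly on local practice. Different re-swabbing habits could therefore show up as differences in positivity. Co-infection is reported in the same sample-based sentence, and a count of samples positive for two or more pathogens may differ from the number of patients meeting 3.6.4.

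**Working it through.** **Step 1. Which unit does Table 4 use?** Inputs from 3.10: 22 × 300 = 6,600 patients, and 6,600 × 0.90 = 5,940. The hospitals in Table 1 also sum to 22. The Clopper-Pearson limits are the 0.025 quantile of Beta(x, n − x + 1) and the 0.975 quantile of Beta(x + 1, n − x). The half-width is (upper − lower)/2, with n = 5,940 and x = np rounded.

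| Pathogen | Prevalence | Table 4 | Recomputed |
|---|---|---|---|
| COVID | 20% | 1.025% | 1.0255% |
| COVID | 25% | 1.109% | 1.1094% |
| RSV | 2% | 0.365% | 0.3651% |
| RSV | 7% | 0.657% | 0.6575% |
| Influenza | 7% | 0.657% | 0.6575% |
| Influenza | 12% | 0.835% | 0.8349% |

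All six agree to within 0.001 of a percentage point. The alternatives do not fit at 20%: a Wald interval at 5,940 gives 1.017%, and Clopper-Pearson at 6,600 gives 0.973%. Table 4 is therefore a patient-level calculation with one independent result per patient.

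**Step 2. How far could a sample count move the estimate?** The repeat rates here are assumptions, because the protocol gives none. Let p be the patient-level prevalence under 3.6.3, a and b the shares of positive and negative patients swabbed twice, and c the chance that a positive patient's second swab is also positive.

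Sample proportion = p(1 + ac) / [p(1 + a) + (1 − p)(1 + b)]

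- p = 20%, a = 0.2, b = 0.1, c = 1: 0.24 / (0.24 + 0.88) = 21.4%, a shift of +1.4 points.
- p = 20%, a = 0.1, b = 0.2, c = 1: 0.22 / (0.22 + 0.96) = 18.6%, a shift of −1.4 points.
- p = 20%, a = b = 0.2, c = 0.8: 0.232 / 1.20 = 19.3%, a shift of −0.7 points from discordant swabs alone.
- p = 20%, a = b, c = 1: 20.0%, no shift.
- a = b = 0: no shift at any p.
- RSV at p = 2%, c = 1: the first two patterns give 0.024 / 1.102 = 2.18% and 0.022 / 1.198 = 1.84%.

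At 20% the first two shifts exceed the stated 1.025 points and the third does not. The RSV shifts (+0.18 and −0.16 points) lie inside the stated 0.365.

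**Step 3. What happens to the interval?** Suppose a share f of all patients is swabbed twice, with within-patient correlation ρ (both assumed). The variance relative to a binomial on the sample count is

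DEFF = [(1 − f) + f(2 + 2ρ)] / (1 + f)

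and the coverage of a nominal 95% interval is about 2Φ(1.96/√DEFF) − 1.

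| f | DEFF (ρ = 0.6 to 1.0) | Coverage |
|---|---|---|
| 0.1 | 1.11 to 1.18 | 93.7% to 92.9% |
| 0.2 | 1.20 to 1.33 | 92.6% to 91.0% |
| 0.5 | 1.40 to 1.67 | 90.2% to 87.1% |

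For example, f = 0.2 and ρ = 1 give (0.8 + 0.8)/1.2 = 1.33. With f = 0, DEFF is 1 and coverage is unaffected.

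**The case against.** The best defence is that the sample wording is loose and patients are meant. Section 3.5 places the primary outcome in patients, 3.6.3 resolves it per patient, 3.10 restates the objective per patient, and the heading of 3.13.2 speaks of SARI numbers. Section 3.13 leaves the detailed analyses and table shells to the SAP, which may say how repeat samples are handled. The study is descriptive and tests no hypothesis.

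Much of this stands, and it shows which way to reconcile the text. It does not remove the conflict. The operative wording says samples in the objective, in the abstract and in the analysis section, and a SAP can only follow one unit by departing from the other.

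Three stronger readings are tempting, and the protocol does not support them.

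- **That the reported proportions will be biased, or that sicker patients will be over-counted.** Repeat swabs are allowed, but nothing says how often they occur or who is re-sampled.
- **That the incidence estimates inherit the error.** Section 3.13.5 specifies the percentage of patients testing positive, so its formula does not draw on the sample figure. The estimate is also exploratory and conditional on feasibility.
- **That co-infection has no sample-level proportion at all.** Section 3.6.4 refers to any respiratory sample, and samples positive for two or more pathogens can be counted. The narrower point, that this count may differ from the patient-level one, is what holds.

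**Conclusion.** The contradiction in unit is explicit and concerns the first primary objective; that is the reason to correct it. No bias has been demonstrated. Read literally, the sample rule conflicts with 3.6.3 wherever a patient's swabs disagree, does not estimate the quantity for which Table 4 was computed, and gives intervals that ignore within-patient correlation.

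The size rests entirely on assumed repeat rates. It is nil with one sample per patient, about 1.4 points either way at 20% prevalence under the unequal rates shown, and a loss of roughly 1 to 8 points of coverage when 10% to 50% of patients are swabbed twice. The direction depends on whether positive or negative patients are re-swabbed more often and on how often swabs disagree. Table 4 itself is correct for a per-patient proportion in which all 5,940 patients are tested.

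**What to change.** Reword objective 1 (title page, abstract and 2.1), section 3.13.2 and the matching sentence in the abstract's statistical analysis. The primary proportion becomes the number of SARI patients, one record per SARI episode, with a laboratory-confirmed infection as defined in 3.6.3, divided by the number tested for that pathogen, with exact binomial 95% intervals. The denominator has to be specific to the pathogen because 3.8 makes only SARS-CoV-2, influenza and RSV testing a minimum. Report co-infection per patient under 3.6.4.

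If sample-level positivity is still wanted as a laboratory table, either present it as descriptive only or give it intervals that account for clustering within patient. Both are valid.

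The cost is wording in the protocol and agreement with the SAP table shells. No new data are needed. If all 5,940 patients are tested, the Table 4 precision stands as stated.
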